# **6 DISCONTINUATION**

## **6.1 Discontinuation of Individual Subject(s)**

A discontinuation is a subject who enrolled in the study and for whom study treatment is permanently discontinued prematurely for any reason.

The subject is free to withdraw from the study treatment and/or study for any reason and at any time without giving reason for doing so and without penalty or prejudice. The

investigator is also free to terminate a subject's involvement in the study at any time if the subject's clinical condition warrants it.

If a subject is discontinued from the study with an ongoing AE or an unresolved laboratory result that is significantly outside of the reference range, the investigator will attempt to provide follow-up until the condition stabilizes or no longer is clinically significant.

The subject will be discontinued from treatment if any of the following occurs:

- Subject develops objective disease progression per RECIST v.1.1 criteria based on investigator assessment.
- Subject develops clinical progression (if objective disease progression is not evaluated).
- Subject develops a Grade 4 or unacceptable AE as assessed by the Investigator (Refer also to Section 5.6.2.1.3 and Section 5.6.5.2.1)
- Investigator decides that it is in the subject's best interest to discontinue.
- Subject declines further study participation (i.e., study withdrawal).
- A significant protocol deviation or non-compliance occurs with a subject that compromises study objectives or subject safety.
- Subject is lost to follow-up despite reasonable efforts by the Investigator to locate the subject.
- The study is terminated by the Sponsor.

The Medical Monitor must be contacted before a subject is discontinued from study treatment for reasons other than objective disease progression per RECIST v.1.1.

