## **7.7 Protocol Deviations and Other Analyses**

Protocol deviations, as defined in Section 8.1.6 will be summarized for all randomized subjects by treatment group and total as well as by site. A data listing will be provided by site and subject.

The protocol deviation criteria will be uniquely identified in the summary table and listing. The unique identifiers will be as follows:

PD1 - Entered into the study even though they did not satisfy entry criteria,

PD2 - Developed withdrawal criteria during the study and was not withdrawn,

PD3 - Received wrong treatment or incorrect dose,

PD4 - Received excluded concomitant treatment.

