5.2. PER PROTOCOL ANALYSIS SET [PPS]

The per-protocol analysis set (PPS) will consist of all subjects in the FAS who did not experience protocol deviations that might affect the efficacy endpoints. Important protocol deviations that might affect efficacy are defined separately for each version of the protocol, as the inclusion/exclusion numbering may change between versions. Specifically, subjects are expected to be excluded from the PPS due to the following reasons:

- PD1 - Did not meet the inclusion/exclusion criteria that are prognostic of the efficacy endpoints; i.e., one or more of:
 - Original Protocol, Amendment 1, Amendment 2, or Amendment 3: Inclusion Criteria 3, 4, 5, 7, 9, 10 or Exclusion Criteria 1, 2, 3, 4, 5, 6, 8, 9, 10, 11, 12, 14.
- PD2 Developed withdrawal criteria during the study and was not withdrawn.
- PD3 - Received wrong treatment or incorrect dose
 - Did not receive treatment
 - Not treated as assigned (i.e., received the wrong drug)
- PD4 – Received excluded concomitant treatment
 - Prohibited concomitant medication [see SAP Appendix 3]
 - Prohibited non-drug therapy [see SAP Appendix 3]

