17.1.4.1. Sensitivity to Analysis Set

Methods used for the primary analysis of the primary PFS endpoint will be used in the PPS to investigate the sensitivity to analysis set (i.e., sensitivity to major protocol deviations) and robustness of the primary analysis results. The Censoring Rules (Set 1) apply.

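### SAP 5.2 excludes subjects from the per-protocol set for not being withdrawn, with no time limit; where the withdrawal criterion is RECIST progression, this usually deletes an observed PFS event

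*SAP*

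**What the plan says.** SAP 5.2 defines the PPS as those FAS subjects "who did not experience protocol deviations that might affect the efficacy endpoints". It then lists the deviations expected to lead to exclusion, one of which is "PD2 Developed withdrawal criteria during the study and was not withdrawn". The wording matches the deviation category in Protocol 7.7, "PD2 - Developed withdrawal criteria during the study and was not withdrawn". The neighbouring categories are narrowed in the SAP: PD1 to numbered eligibility criteria, PD3 to subjects who were untreated or received the wrong drug. PD2 is limited neither by criterion nor by date.

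Neither document has a list titled withdrawal criteria. The matching list is in Protocol 6.1, on discontinuation of treatment. It opens with "Subject develops objective disease progression per RECIST v.1.1 criteria based on investigator assessment". It also includes clinical progression, "Subject develops a Grade 4 or unacceptable AE as assessed by the Investigator", and significant deviation or non-compliance.

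SAP 17.1.4.1 sets the role of the PPS for PFS: "Methods used for the primary analysis of the primary PFS endpoint will be used in the PPS", with Censoring Rules Set 1. SAP 17.2.3 runs every secondary efficacy endpoint, including OS, in the PPS as well. SAP 17 keeps the FAS as the primary set.

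**The concern.** Investigator RECIST progression is both a reason to stop treatment and the event that ends PFS. A subject who progresses and is not withdrawn commits the PD2 deviation once the PFS time is already fixed. Removing that subject selects PPS membership on the outcome.

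The PPS analysis of PFS is the planned check on sensitivity to major deviations. If the rule deletes events from one arm more than the other, the PPS hazard ratio moves in favour of the arm that loses more events. A difference between FAS and PPS could then reflect the deletion rather than non-adherence. The trial is open-label, and one drug is taken orally twice a day while the other is infused every 3 weeks. Unequal numbers are therefore possible, but the documents give no counts and no direction.

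**Working it through.** **Sequence of dates on the RECIST branch**

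1. PFS ends at the earlier of investigator-documented RECIST progression or death (SAP 17.1.1). Set 1 dates a progression at the assessment that showed it (SAP 17.1.2.1, Table E).
2. Protocol 6.1 makes that same finding a criterion for stopping treatment.
3. PD2 needs the criterion to be met and the subject then not to be withdrawn. The deviation therefore falls at or after the date in step 1.
4. It cannot affect investigator PFS, so it fails the test in SAP 5.2, yet PD2 as written still excludes the subject.

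**The plan's design figures reproduce.** Inputs from SAP 3.5: hazard ratio 0.667, one-sided alpha 0.1, power 80%, 1:1 allocation.

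- Events = 4(1.2816 + 0.8416)² / (ln 0.667)² = 18.03 / 0.164 ≈ 110, as stated.
- Largest significant hazard ratio = exp(−1.2816 × 2/√110) = 0.783, as stated.

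Both figures belong to the FAS analysis and are not affected by PD2.

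**Loss of events in the PPS.** With k events removed, power = Φ(|ln HR| × √(110 − k)/2 − 1.2816) at a hazard ratio of 4/6. This gives 79.3% for k = 3, 78.7% for k = 5, 77.2% for k = 10 and 74.0% for k = 20. The values of k are assumptions. The loss of information is small, so imbalance between arms matters more.

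**Effect of imbalance.** Simulation: 134 subjects at 7 per month, exponential PFS, control median 4 months, cut-off at event 110, unstratified log-rank test, 4,000 trials per row. A share of subjects with events is deleted to form the PPS. The shares are assumptions. Monte Carlo error on a rejection rate is about 0.5 percentage points. True hazard ratio 1:

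| Events deleted from PPS | Mean number deleted | FAS HR; rejection | PPS HR; rejection |
|---|---|---|---|
| 5% in both arms | 5.5 | 1.00; 10.0% | 1.00; 9.8% |
| 10% in both arms | 11.0 | 1.00; 10.0% | 1.00; 10.1% |
| 10% AGS-16C3F, 5% axitinib | 8.3 | 1.00; 9.9% | 0.98; 11.3% |
| 10% AGS-16C3F only | 5.5 | 1.00; 10.6% | 0.97; 13.7% |
| 20% AGS-16C3F only | 11.0 | 1.00; 10.1% | 0.94; 17.5% |
| 10% axitinib only | 5.5 | 1.01; 10.4% | 1.04; 8.0% |

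At a true hazard ratio of 0.667 the shifts are: 10% in both arms, 0.657 to 0.648; 10% of AGS-16C3F only, 0.661 to 0.637; 20% of AGS-16C3F only, 0.661 to 0.611; 10% of axitinib only, 0.664 to 0.680.

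**Worst case.** Two further simulations (1,200 and 1,500 trials per scenario) added 8-week scans with 67 subjects per arm. Under a true hazard ratio of 1, deleting 5 AGS-16C3F subjects who all progressed at the first scan gave 0.91 and 0.93, with rejection of 21% and 20%. Deleting 5 AGS-16C3F subjects who progressed at any scan gave only 0.97 and 0.98.

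**The case against.** **PD2 is wider than progression.** A reader might infer that PD2 can only follow the PFS event. The documents do not support that. Clinical progression, a Grade 4 or unacceptable adverse event, and non-compliance are on the same list, are not Set 1 events and can come earlier. Those exclusions are legitimate and should stay.

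**Not every exclusion on the RECIST branch removes an event.** Set 1 censors a progression that follows two or more consecutive missed assessments, or that comes after non-protocol anticancer treatment. For PFS by central review, investigator progression is not the event at all.

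**Treating past progression is not an investigator option.** Protocol 6.1 requires discontinuation at progression, and Protocol 8.1.6 makes failure to withdraw a notifiable deviation. The documents give no reason to expect it often, or more in one arm. Nor does one dose between a scan and the decision to stop, followed by withdrawal, clearly meet PD2.

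**Exclusion is not wholly automatic.** SAP 5.2 says subjects are expected to be excluded, SAP 5 leaves membership to the sponsor, and Protocol 7.2 refers to Classification Specifications that are not among these documents. The sponsor could keep such a subject under the general test. This softens the point but does not remove it: the written rule names the exclusion, and case-by-case relief in an open-label trial would be decided after the subject's progression is known.

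**OS differs.** Treatment past progression precedes death and could affect it, so exclusion is defensible in the PPS analysis of OS.

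**Conclusion.** Wrong as written, for one branch of PD2 and for PFS. Where the unmet withdrawal criterion is investigator RECIST progression, exclusion usually deletes an observed event for a deviation that cannot have affected investigator PFS, contrary to SAP 5.2's own principle.

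The size depends on counts that the documents do not give. Under a true hazard ratio of 1, the assumed range runs from no bias (equal shares deleted) to a PPS hazard ratio of about 0.97–0.94 with 14–18% rejection (10–20% of AGS-16C3F events only). In the opposite direction it is about 1.04 with 8% (10% of axitinib events only). A reader might take a doubling of false positives to about 20% as the expected effect. That figure needs every deleted subject to be in the AGS-16C3F arm and to have progressed at the first scan, and nothing in the documents supports either condition. All the simulations are unstratified, whereas the planned test is stratified.

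A reader might also infer that the trial's conclusion is at risk. It is not: the primary analysis is in the FAS, no decision rule rests on the PPS p-value, and the FAS sensitivity analyses under Sets 2 to 4 do not use PPS membership.

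**What to change.** In SAP 5.2, state that for the PPS analyses of PFS, PD2 excludes a subject only if the withdrawal criterion was met, and treatment continued, before that subject's PFS event or censoring date. Continued treatment after RECIST progression stays in the deviation table under Protocol 7.7 but does not exclude the subject from PPS PFS. State separately whether PD2 for treatment past progression still applies to the PPS analysis of OS, where the deviation precedes the endpoint.

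The cost is a short addition to SAP 5.2, a date comparison at classification, an endpoint-specific PD2 flag and a slightly larger PPS for PFS. No treatment rule changes.

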5.3. SAFETY ANALYSIS SET [SAF]

The safety analysis set (SAF) will consist of all randomized subjects who receive at least one dose of study drug (AGS-16C3F or axitinib). Subjects will be classified according to actual study treatment received for the first dose. If there is any doubt whether a subject was treated or not, they will be assumed to have been treated for the purposes of analysis.

The SAF will be used for summaries of all safety variables.

5.4. PHARMACOKINETIC ANALYSIS SET [PKAS]

The pharmacokinetic analysis set (PKAS) will consist of subjects who were randomized to receive AGS-16C3F and who have sufficient serum concentration data to facilitate derivation of at least one PK parameter, and for whom the time of dosing on the day of sampling is known. Additional subjects may be excluded from the PKAS at the discretion of the pharmacokineticist. Any formal definitions for exclusion of subjects or time-points from the PKAS will be documented in the Classification Specifications and determined in the Classification Meeting.

5.5. PHARMACODYNAMIC ANALYSIS SET [PDAS]

A pharmacodynamic marker has not been established for this target.

6. GENERAL CONSIDERATIONS

6.1. STUDY PERIODS

This study has several periods that are defined for analysis as follows:

- Screening: Prior to first dose of study medication; may include pre-screening and screening
- Treatment: From the date of first dose of study drug through the date of last dose or date of decision to end treatment.
- Safety Follow-up: The post-treatment follow-up period which extends from the date of last dose + 1, or the date of decision to end treatment + 1, through the later of the Safety Follow-up visit or (the date of last dose/decision to end treatment plus 28 days).
- Survival Follow-up: From the later of the Safety Follow-up visit or (the date of last dose/decision to end treatment plus 28 days) to death or study closure.

6.2. REFERENCE START DATE AND STUDY DAY

The study day (or “relative day”) will be calculated from the reference start date, and will be used to show start/stop day of assessments and events.

The reference start date is the date of the first dose of study drug. Day 1 is the study day of first dose of study drug. The study day is calculated as shown below, and may appear in listings where an assessment date or event date appears.

- If the date of a visit, assessment, or event is on or after the reference date then study day = (date of event – reference date) + 1.
- If the date of a visit, assessment, or event is prior to the reference date then study day = (date of event – reference date).

In the situation where the date of a visit, assessment, or event is partial or missing, the partial date(s) will be displayed but the study day and any corresponding durations will be missing from the listing(s), unless otherwise specified for a particular display.

6.3. BASELINE

On Cycle 1 Day 1 [C1D1], all procedures other than post-infusion specific procedures must be performed before the first dose of study drug is administered. Subjects must meet all inclusion/exclusion criteria at C1D1, including the results from all predose procedures occurring on C1D1.

Baseline is defined as the last non-missing measurement taken within 28 days prior to reference start date (including unscheduled assessments), unless otherwise specified. In the case where the last non-missing measurement and the reference start date coincide, that measurement will be considered pre-treatment; but Adverse Events (AEs) and medications commencing on the reference start date will be considered post-baseline.

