### **5.6 Safety Assessment**

#### **5.6.1 Vital Signs**

Measurements consisting of blood pressure, heart rate, respiration rate, and temperature will be collected throughout this trial. Vital signs will be collected according to the schedule displayed in [Table 1](#)

- For subjects randomized to AGS-16C3F, on the days of study drug administration, vital signs will be taken predose, and approximately 30 minutes after administration of study drug
- For subjects randomized to axitinib, vital signs will be taken once at each clinic visit

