6.4. DERIVED TIMEPOINTS

For subjects in the AGS-16C3F group, each infusion date starts a new cycle. Cycles are numbered consecutively. For subjects in the axitinib group, clinic visits and most other events are identified by the planned study day.

The following derived visit definitions will apply to tables, figures, and listings unless otherwise specified for a particular analysis:

- **Worst Post-Baseline:** The worst value collected in the period from C1D1 post-dose through the later of the safety follow-up visit or the last dose date + 28 days (inclusive).
- **Safety Follow-Up:** Everyone is required to have an actual safety follow up visit and one measurement for the safety f/u. For subjects who don't have a safety F/U visit, report the worst value recorded during the period from the day of last dose or decision to end treatment through the subject's last available assessment.
- **Final Visit:** The chronologically last available assessment.
- **Any Time during Treatment/Safety Follow-up:** From C1D1 post-dose through the later of the safety follow-up visit or the last dose date + 28 days (inclusive).

Eye assessments are identified in the raw data only by the exam date. Data from the AGS-16C3F subjects will be assigned to a Cycle based on comparing the exam date to the infusion dates. Data from the axitinib subjects will be assigned to a scheduled assessment or identified as a PRN exam, based on the calculated study day of the exam (see Section 6.6, Visit Windowing Conventions).

For tables that show eye-related safety results by timepoint during the study, data from the AGS-16C3F subjects will be grouped for analysis as follows: Day 43 will include data recorded from post-dose C1D1 through Predose C3D1, inclusive; Day 106 will include data recorded from Post-dose C3D1 through Predose C6D1, inclusive; subsequent intervals will be defined similarly at 3-cycle intervals during treatment. For the axitinib subjects, the analysis periods are based on the scheduled/PRN classifications that have been assigned. For both groups, assessments that are made after the end of treatment (EOT) will be grouped together as "EOT and beyond". Both planned and PRN eye assessment data will be included in all intervals.

It may be necessary to derive other timepoint records for some analyses. Where applicable, these are specified for each analysis that requires them.

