19.4. ECG EVALUATIONS

19.4.1. ECG ASSESSMENTS

Subjects will have an ECG at screening, on C1D1, and at the end of study safety follow-up visit. Subjects who are randomized to AGS-16C3F will have an ECG at predose and at 2 hours post-dose on C1D1; subjects randomized to receive axitinib will have an ECG at predose only, on C1D1.

ECGs are done in triplicate for all timepoints, approximately 3-5 minutes between each assessment. Each set of results will be identified by a unique recorded clock time. The triplicate values may be considered individually or represented by their median, depending on the analysis. Retests and unscheduled assessments will be included, unless otherwise specified.

The following ECG parameters will be reported for this study:

- HR (bpm)
- PR Interval (msec)
- QRS Interval (msec)
- QT Interval (msec)
- QTcF Interval (msec) [derived]
- Overall assessment of ECG (Investigator's judgment):
 - o Normal
 - o Abnormal, Not Clinically Significant (ANCS)
 - o Abnormal, Clinically Significant (ACS)

Any ECG-related adverse events that are determined by the investigator or medical reviewer to have occurred will be collected on the Adverse Event CRF and reported in the AE tables, listings, and figures.

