19.4.4. ECG ANALYSIS METHODS

The ECG quantitative data will be summarized by incidence of treatment-emergent Grade 3 or Grade 4 QTcF values by treatment arm. Grade 3 and Grade 4 values will be identified prior to averaging the triplicate ECG results.

Subjects who met the abnormal criterion specified in Section 19.4.3 will be identified on the ECG data listing.

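### SAP 6.3 does not require that a same-day baseline value be predose, so read literally it takes the 2-hour post-infusion ECG as baseline in the AGS-16C3F arm only, in conflict with SAP 6.4

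*SAP*

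**What the plan says.** SAP 6.2 fixes the reference point as a calendar date without a clock time: "The reference start date is the date of the first dose of study drug". SAP 6.3 then gives the general rule: "Baseline is defined as the last non-missing measurement taken within 28 days prior to reference start date (including unscheduled assessments), unless otherwise specified". For a value dated on that same day it adds: "In the case where the last non-missing measurement and the reference start date coincide, that measurement will be considered pre-treatment". The rest of that sentence treats adverse events and medications starting on the day as post-baseline, but says nothing of measurements taken after the dose.

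The same section shows that such measurements exist, because it opens by stating that on Cycle 1 Day 1 "all procedures other than post-infusion specific procedures must be performed before the first dose of study drug is administered".

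SAP 6.4 defines the worst post-baseline value as: "The worst value collected in the period from C1D1 post-dose through the later of the safety follow-up visit" or 28 days after the last dose. That window begins after the first dose on Cycle 1 Day 1.

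For ECGs, SAP 19.4.1 states: "Subjects who are randomized to AGS-16C3F will have an ECG at predose and at 2 hours post-dose on C1D1". Axitinib subjects have a predose ECG only on that day. SAP 19.4.4 plans one quantitative summary: "The ECG quantitative data will be summarized by incidence of treatment-emergent Grade 3 or Grade 4 QTcF values by treatment arm". The grades come from Table K in SAP 19.4.3, where one limb of Grade 4 is a change from baseline of more than 60 ms. No part of SAP 19.4 defines an ECG baseline.

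**The concern.** The same-day sentence in 6.3 is the only text that lets any Cycle 1 Day 1 value serve as baseline, because the general rule asks for a value before the reference date. It selects by date and by the word last. In the AGS-16C3F arm the last scheduled ECG on that date is the one taken after the infusion. A programmer who follows 6.3 as written would use an on-drug ECG as baseline in the investigational arm and a predose ECG in the comparator arm. One who follows 6.3 and 6.4 together would use the same ECG as both baseline and a post-baseline value.

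The 2-hour ECG is the only scheduled ECG after the first AGS-16C3F dose and before Safety Follow-Up, which Protocol 5.2.7 places at least 28 days after the last dose. If it is its own baseline, an acute QTcF increase cannot register as a change. At stake is the one quantitative ECG comparison in the SAP, with an error confined to one arm.

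**Working it through.** The plan states no figure on this point, so there is none to reproduce. The check applies the written rules to the ECG schedule.

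**Which ECG becomes baseline** (schedule from SAP 19.4.1 and Protocol 5.6.4)

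| Arm | ECGs up to and including the first-dose date | Last on that date = literal 6.3 baseline | Status under 6.4 |
|---|---|---|---|
| AGS-16C3F | screening, predose, 2 h after infusion | 2 h after infusion | post-baseline |
| Axitinib | screening, predose | predose | not in the post-dose window |

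The two sections agree for axitinib and conflict for AGS-16C3F. SAP 6.5 says that triplicate ECGs are not retests and refers their handling to 19.4, which is silent on baseline. Treatment-emergent is defined in SAP 19.1 for adverse events, not for ECG values.

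**Effect on change from baseline**

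Let p, h and f be the median QTcF at predose, 2 hours and follow-up.

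- 2-hour change: h − p with a predose baseline; h − h = 0 under literal 6.3.
- Follow-up change: f − p with a predose baseline; f − h = (f − p) − (h − p) under literal 6.3. The error equals the 2-hour effect with its sign reversed, so a 2-hour rise hides a later rise and a 2-hour fall exaggerates one.

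**Effect on Table K grades**

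The numeric rules are Grade 1 for 450–480 ms, Grade 2 for 481–500 ms, Grade 3 for two of three values at 501 ms or more, and Grade 4 for a median of 501 ms or more or a change above 60 ms. Only the last limb uses baseline. The documents give no QTcF data, so the values below are assumed, with all three readings in a triplicate equal.

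| Case | p, h, f (ms) | 2 h, predose baseline | 2 h, literal 6.3 | Follow-up, predose baseline | Follow-up, literal 6.3 |
|---|---|---|---|---|---|
| A | 420, 485, 425 | +65, Grade 4 | 0, Grade 2 | +5, none | −60, none |
| B | 420, 510, 425 | +90, Grade 4 | 0, Grade 4 | +5, none | −85, none |
| C | 430, 470, 435 | +40, Grade 1 | 0, Grade 1 | +5, none | −35, none |
| D | 420, 440, 485 | +20, none | 0, none | +65, Grade 4 | +45, Grade 2 |

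The literal-6.3 grades at 2 hours assume that the value still counts in the 6.4 window. Case A loses its flag at 2 hours and case D at follow-up, so both leave a table restricted to Grades 3 and 4. Case B keeps Grade 4 because its absolute value qualifies.

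A grade is lost at 2 hours only if h − p is above 60 ms and h is below 501 ms, which requires p below 501 − 60 = 441 ms.

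**Number exposed**

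With 134 subjects randomized 1:1, 134 / 2 = 67 would be in the AGS-16C3F arm. This counts subjects whose baseline is open to the two readings, not subjects whose grade would change.

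**The case against.** The strongest reply is that this is a missing word. SAP 6.3 opens by separating predose from post-infusion procedures, so the same-day sentence can be read as a tie-break that keeps predose values from being rejected for carrying the date of Day 1. SAP 6.4 places post-dose values from that day after baseline. SAP 19.4.1 records a clock time for each ECG, so the two triplicates can be told apart. This stands to the extent that the intended baseline is probably predose. It does not remove the problem: 6.4 defines post-baseline windows without redefining baseline, and the operative sentence in 6.3 carries no predose condition.

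A reader might go further and infer that the 2-hour ECG definitely is the baseline and that any acute QTcF effect therefore disappears from the by-arm table. The documents do not support that. Section 6.4 points the other way. The criteria at 501 ms or more are absolute, so a 2-hour value of that size keeps its grade. It would leave the treatment-emergent count only if 6.3 were also taken to make it pre-treatment for that table, which the SAP does not say.

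A reader might also extend the point to vital signs, since in the AGS-16C3F arm "vital signs will be taken predose, and approximately 30 minutes after administration of study drug". In SAP 19.5.3, however, the only change-from-baseline summary is body weight, which SAP 19.5 records predose; the other vital signs are only listed. Protocol 7.5.3 does mention vital-sign changes from baseline, so the issue would return if those tables were produced.

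Finally, SAP 19.4.3 makes the computed grade provisional, with the investigator deciding on any adverse event, and the ECG listing shows the values. These safeguards limit the harm but do not correct the summary table.

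**Conclusion.** The point holds as a conflict between SAP 6.3 and 6.4 that SAP 19.4 leaves open. Followed literally, 6.3 gives a wrong baseline in the AGS-16C3F arm only. The consequence is limited to the Table K limb for a change above 60 ms, which cannot be met at 2 hours, and to Safety Follow-Up changes, which are off by the size of the 2-hour effect. The absolute criteria, the vital-sign summaries planned in the SAP and PFS are not affected.

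The size in practice is unknown because the documents contain no QTcF data, and the examples rest on assumed values. The conclusion also assumes that the ECGs are done as scheduled and that no programming specification outside these documents already sets a predose baseline. SAP 19 plans no between-arm tests of safety data unless otherwise specified, so the issue concerns a descriptive table. It should still be corrected, because it can lower the count of flagged QTcF changes in the investigational arm alone.

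**What to change.** Amend SAP 6.3 to say that:

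- baseline is the last non-missing measurement before the date and time of first dose; where no clock time exists, a value from that date counts only if its nominal time point is predose;
- measurements taken after the infusion on Cycle 1 Day 1 are post-baseline, in line with SAP 6.4.

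Add to SAP 19.4 that ECG baseline is the median of the Cycle 1 Day 1 predose triplicate, or of the screening triplicate if that is missing.

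The cost is a few sentences. ECG clock times are recorded (SAP 19.4.1), and infusion start times are held in the study database although they are not tabulated (SAP 22). No new data are needed. If the ECG table has already been programmed, confirm which triplicate was used as baseline and rerun it if it was the 2-hour one.
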